Level -1	Mitoxantrone10 mg/m ²	Sorafenib 200 mg once daily

In addition to safety stopping rules in phase 1, we will also employ efficacy stopping rules to make sure that the regimen does not have lower response rates than our current standard. Among the first 57/61 evaluable patients treated with G-CLAM alone in our ongoing phase 1/2 study, the MRDneg CR rate was 68%. We will assume that the G-CLAM+sorafenib regimen will not be of further interest if the true MRDneg CR rate is 60% or less (null hypothesis) and that that an MRDneg CR rate of 80% or more would be of interest for further investigation (alternative hypothesis). Therefore, if MRDneg CR is seen in < 5 of the first 11 patients, consideration will be given to stopping the study. An 80% confidence interval for an MRDneg CR rate of 4/11 is 0.17-0.60. Thus the upper bound of this limit is less than the current MRDneg CR rate with G-CLAM alone (68%). However, because the first 11 G-CLAM + sorafenib patients may differ with respect to cytogenetics/age etc. from the original 57 G-CLAM patients, a decision to stop would also depend on comparative examination of patient characteristics.

14.2 Phase 2

The study will be conducted in two sequential parts. The phase 1 portion ends once an MTD is identified or dose level 6 has been completed, whichever occurs first. Patients enrolled in the Phase 1 portion and treated at the MTD dose of sorafenib and mitoxantrone will be included in the analysis of the Phase 2 portion. The primary objective of the Phase 2 portion is to evaluate the MRDneg CR rate after up to 2 courses of induction chemotherapy.

A two-stage design will be used (Simon Optimal Two-Stage). As per the phase 1 section above, the MRDneg CR rate of our historical control of G-CLAM alone is 68%. G-CLAM+sorafenib will not be of further interest if the true MRDneg CR rate is 60% or less (null hypothesis) and that that an MRDneg CR rate of 80% or more would be of considerable interest for further investigation (alternative hypothesis). Therefore, in the first stage, 19 eligible patients will be accrued. If necessary, the study may be temporarily closed while remission data is collected. If at least 12 of the first 19 patients achieved an MRDneg CR (63%), we will move to the second stage. The second stage would enroll another 22 patients (for a total of 41), with G-CLAM + sorafenib considered of interest (at least 80% MRDneg CR rate) if at least 31/41 attained

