MRDneg CR. The probability of declaring a therapy of interest when it is not is 10% (type-1 error), and not of interest when it is, is 20% (power 80%). Under the null hypothesis (true MRDneg CR rate 60%) the probability of termination before enrolling 41 patients is 51% and the average sample size is 29 patients. Note that patients treated at the recommended sorafenib and mitoxantrone doses during the Phase 1 part of the study would count toward the first 19 patients. Patients will be considered not evaluable if they received less than 75% of the assigned doses of each chemotherapeutic agent during Cycle 1, and they will be replaced. If a patient does not receive at least 75% of their assigned dose of sorafenib but discontinues the drug due to toxicity, they will be considered evaluable as we want to capture this essential toxicity data (and its potential downstream effect on efficacy) and not be replaced.

QOL scores, resource utilization, and cost variables will be recorded and summarized using descriptive methods including boxplots, histograms, and statistical summary measures (medians, means, standard deviation, N, and proportions). This study will not be powered to detect statistically significant differences between these endpoints for those with different responses; rather we will record these outcomes to inform a subsequent larger study, should follow up investigations be warranted.

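### The phase 2 rule (12/19, then 31/41) has a type I error of 2.7% at the stated 60% null, not 10%, and is not the Simon optimal design for the stated inputs

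*Combined protocol and SAP*

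**What the plan says.** All of the design is in Section 14.2 (Phase 2) of the combined protocol and SAP.

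- Design type: "A two-stage design will be used (Simon Optimal Two-Stage").
- Null and alternative for the primary endpoint: "60% or less (null hypothesis) and that that an MRDneg CR rate of 80% or more would be of considerable interest".
- Stage 1 size: "in the first stage, 19 eligible patients will be accrued". Rule for continuing: "If at least 12 of the first 19 patients achieved an MRDneg CR (63%), we will move to the second stage".
- Stage 2 size: "The second stage would enroll another 22 patients (for a total of 41"). Final rule, counting responders over both stages: "considered of interest (at least 80% MRDneg CR rate) if at least 31/41 attained".
- Type I error: "The probability of declaring a therapy of interest when it is not is 10% (type-1 error"). Type II error, put as the chance of missing a useful regimen: "not of interest when it is, is 20% (power 80"%).
- Under the null, named there as 60%, the plan gives a 51% chance of stopping before 41 patients and an average sample size of 29.

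The same section gives the centre's historical rate with G-CLAM alone as 68%.

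**The concern.** A Simon design is fixed by four inputs (null rate, alternative rate, type I error, power), and the cut-offs follow from them. Here the final cut-off looks too high for the stated error. Under a 60% null the expected count in 41 patients is 0.60 × 41 = 24.6, with a standard deviation of √(41 × 0.60 × 0.40) = 3.14. A threshold of 31 is about two standard deviations above that, which suggests an error of roughly 2 to 3%, not 10%. The sample size also looks large for a gap of 60% against 80% at 10% error and 80% power.

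What is at stake is the meaning of the primary phase 2 result (objective 2.1.2). If the stated error does not belong to the stated null and cut-off, a reader cannot tell which hypothesis is being tested or how strong a positive result is. A report that copies the sentence would publish an operating characteristic that the trial does not have.

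**Working it through.** **Inputs (all from Section 14.2).** Null 0.60; alternative 0.80; stage 1 of 19 patients, continue with at least 12; stage 2 of 22 patients, 41 in total; declare interest with at least 31.

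**Formulas.** With X₁ ~ Bin(19, p) and X₂ ~ Bin(22, p):

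- Early termination: PET(p) = P(X₁ ≤ 11)
- Expected size: EN(p) = 19 + 22 × (1 − PET)
- Probability of declaring interest: D(p) = Σ over x = 12 to 19 of P(X₁ = x) × P(X₂ ≥ 31 − x)

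**Step 1. Reproduce the plan's own figures.**

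- PET(0.60) = 0.5122; the plan says 51%.
- EN(0.60) = 19 + 22 × 0.4878 = 29.73; the plan says 29, which is this figure truncated.
- D(0.80) = 0.8149; the plan says 80%.

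These agree, so the rule has been read as written.

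**Step 2. Type I error at 0.60.**

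| x of 19 | P(X₁ = x) | P(X₂ ≥ 31 − x) | Product |
|---|---|---|---|
| 12 | 0.1797 | 0.0076 | 0.0014 |
| 13 | 0.1451 | 0.0266 | 0.0039 |
| 14 | 0.0933 | 0.0722 | 0.0067 |
| 15 | 0.0467 | 0.1584 | 0.0074 |
| 16 | 0.0175 | 0.2898 | 0.0051 |
| 17 | 0.0046 | 0.4540 | 0.0021 |
| 18 | 0.0008 | 0.6244 | 0.0005 |
| 19 | 0.0001 | 0.7720 | 0.0000 |

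The sum, from unrounded terms, is D(0.60) = 0.0271. The plan says 0.10.

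**Step 3. Could a nearby reading give 10% at 60%?**

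| Reading | Error at 60% |
|---|---|
| Stage 1 needs 11 of 19, final 31 | 0.0273 |
| Stage 1 needs 13 of 19, final 31 | 0.0257 |
| Single stage, 31 of 41 | 0.0274 |
| Written rule, doubled for two sides | 0.0542 |
| Stage 1 needs 12 of 19, final 30 | 0.0551 (power 0.8915) |
| Stage 1 needs 12 of 19, final 29 | 0.0994 (power 0.9370) |

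No reading with a final cut-off of 31 comes near 10%. Keeping 12/19 and 41 patients, a 10% error corresponds to a final cut-off of 29.

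**Step 4. Where does 10% occur?**

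| Rule | True rate | P(declare) | PET | EN |
|---|---|---|---|---|
| 12/19, 31/41 (written) | 0.65 | 0.1005 | 0.3344 | 33.64 |
| 13/19, 31/41 | 0.65 | 0.0960 | 0.5188 | 29.59 |

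Power at 0.80 is 0.8149 for the first and 0.8002 for the second. An exhaustive search with inputs 65%, 80%, 10% and 20% returns the second row as the Simon *minimax* design. The documents do not say that this is where the numbers came from.

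**Step 5. Is the design Simon optimal for the stated inputs?** An exhaustive search with 60%, 80%, 10% and 20% gives:

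| Design | Continue | Declare | Error | Power | EN at 60% |
|---|---|---|---|---|---|
| Optimal | ≥ 8/11 | ≥ 22/31 | 0.0998 | 0.8076 | 16.9 |
| Minimax | ≥ 7/11 | ≥ 18/24 | 0.0930 | 0.8015 | 17.9 |
| As written | ≥ 12/19 | ≥ 31/41 | 0.0271 | 0.8149 | 29.7 |

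The written design is neither.

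**The case against.** **The error is conservative.** Inputs to a Simon search are ceilings, and 2.7% is below 10%, so false positives at 60% are not inflated. That is true, and it limits the harm. But the sentence gives 10% as the probability itself, not as a limit, and a shortfall this large is not the usual rounding from whole-number cut-offs: 29/41 would use 9.9% of the 10%.

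**The 65% explanation is only partly supported.** With the written 12/19 rule at 65%, early termination is 33% and expected size 33.6, which do not match the stated 51% and 29. All four stated properties fit 65% approximately only if stage 1 requires 13 of 19, and the plan attaches its 51% explicitly to a 60% rate. This stands. The stated figures seem to mix two designs, and the documents do not show whether the null, a cut-off or the error rate slipped. The 65% figure shows where 10% occurs; it does not prove intent.

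**Correcting the sentence leaves 29 and 30 of 41 rejected.** Also true. The correction makes the plan state openly that it applies a stricter test than 10% at 60%; it does not relax that test.

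**The smaller optimal design does not make 41 patients a defect.** Agreed. The comparison shows only that the label is wrong.

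**Conclusion.** The concern holds. For the rule as written, the type I error at the stated 60% null is 2.7%, about a quarter of the stated 10%. Power (81.5%), early termination (51.2%) and expected size (29.7) agree with the plan to within rounding or about 1.5 percentage points, so the 10% is the one figure that fails. A 10% chance of declaring interest belongs to a true rate of 65%. At the 68% historical rate the rule would declare interest 19.0% of the time, so the choice of null matters for interpretation. The Simon optimal label is also wrong for the stated inputs: maximum 41 against 31 patients, expected 29.7 against 16.9 under the null.

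The figures assume a binomial count with a common response rate, all 41 patients evaluable and both cut-offs applied as written. They do not model the replacement of non-evaluable patients.

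**What to change.** Keep 12/19 and 31/41 and replace the error-rate sentence in Section 14.2 with the exact properties: type I error 2.7% at a true rate of 60% (10.0% at 65%), power 81% at 80%, early termination 51% and expected size 29.7 under 60%. Delete the word Optimal. This costs wording only and changes nothing for patients or conduct. It also avoids moving a decision boundary after the fact.

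Before finalising, the trial statistician should check the intended null and the stage 1 cut-off against the original design output. If 65% was intended and the written cut-offs stay, state 65% with its figures: type I error 10.0%, power 81%, early termination 33%, expected size 33.6. That too is wording only. If the check shows that stage 1 was meant to require 13 of 19, correcting it would alter the futility boundary, because 12 of 19 would then stop the study. That would need a formal amendment rather than an edit.

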- 6.3.1 For induction: patients will receive sorafenib and mitoxantrone at 1 of 6 total dose levels as allocated (see section Dose Escalation Scheme page 2 or 15.1.2). Mitoxantrone will be given IV daily over 60 minutes Days 1-3 and sorafenib orally Days 10-19 for all levels. Allowances of +/- 2 days for this window will be allowed for logistical purposes. Levels are as follows: Level 1, mitoxantrone 10 mg/m² with sorafenib 200 mg PO twice daily; Level 2, mitoxantrone 12 mg/m² with sorafenib 200 mg PO twice daily; Level 3, mitoxantrone 15 mg/m² with

sorafenib 200 mg PO twice daily; Level 4, mitoxantrone 18 mg/m² with sorafenib 200 mg PO twice daily; Level 5, mitoxantrone 18 mg/m² with sorafenib 400 mg PO in the morning and 200 mg in the evening; Level 6, mitoxantrone 18 mg/m² with sorafenib 400 mg PO twice daily. Level -1, dosed at mitoxantrone 10 mg/m² and sorafenib 200 mg PO once daily will also be available for dose de-escalation due to toxicities, as described in Section 6.8. For baseline organ dysfunction within the allowable limits of the eligibility criteria, dose reduction of individual medications specific to the organ impairment (e.g. liver, kidney) are allowed but not required, as described in section 6.10, and should be done in conjunction with the Oncology Pharmacist and PI.

- 6.3.2 The dose of mitoxantrone is calculated using the patient's actual weight.
- 6.3.3 For post-remission therapy: sorafenib will be given per dose level as above, starting on day 8 until day 27 or 3 days prior to next cycle of treatment, whichever occurs first. Allowances of +/- 3 days for this window will be allowed for logistical purposes (i.e. timing of clinic visit for count evaluation).
- 6.3.4 For maintenance: sorafenib will be given daily for up to 12 months following post-remission at the final dose the patient received during induction, with subsequent dose adjustment based on blood counts and extra-medullary toxicities.
- 6.3.5 All treatment is given as intent-to-treat; missed doses will not be made up.

6.4 **Administration of G-CSF, Cladribine, and Cytarabine**

- 6.4.1 The doses of the elements of G-CLAM chemotherapy will be as follows: G-CSF 5 µcg/kg rounded to 300 or 480 µcg daily subcutaneously daily on Days 0-5, Cladribine 5 mg/m² IV daily over 2 hours on Days 1-5, and Cytarabine 2 g/m² IV daily over 2 hours on Days 1-5.
- 6.4.2 The doses of G-CSF, cladribine, and cytarabine are calculated using the patient's actual weight.

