- 6.4.3 Days 0 and 1 G-CSF may be omitted at physician discretion for WBC >20,000/µL or signs/symptoms of leukostasis.
- 6.4.4 Administration in the outpatient clinic can be considered but should be discussed with the study investigators.
- 6.4.5 All treatment is given as intent-to-treat; missed doses will not be made up.
- 6.4.6 No investigational or commercial agents or therapies other than those described herein may be administered with the intent to treat the patient's malignancy.

6.5 **Monitoring during/after Induction and Post-Remission Therapy**

For patient monitoring, the following studies and study intervals are suggested:

- 6.5.1 Complete blood counts with differential blood count, including immature cells/blast, and platelet count at least 2 times weekly until ANC >1,000/µL and then at least weekly until platelet count >100,000/µL.
- 6.5.2 Metabolic panel, including bilirubin, ALT/AST, and creatinine at least weekly until ANC >1,000/µL and platelet count >100,000/µL.

- 6.5.3** Blood pressure monitoring on a weekly basis through the first 6 weeks of therapy is recommended. Thereafter, it is recommended that blood pressure should be monitored monthly as long as the patient remains on sorafenib.
- 6.5.4** If patients develop signs or symptoms suggestive of cardiac dysfunction, LVEF should be assessed using the same method to evaluate baseline LVEF status (MUGA scan or echocardiography, or other appropriate diagnostic modality).

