6.9 Maintenance Therapy

- 6.9.1** Patients in MRDneg CR at the end of post-remission therapy with G-CLA+sorafenib can continue to receive sorafenib for up to 12 months, as long as it is tolerated and as long as an MRDneg CR is maintained. Sorafenib will be given daily at the assigned dose level, unless dose reductions are needed for toxicity, in which case that dose would be continued. The MRDneg CR state should be confirmed every 3 months with bone marrow evaluations.

6.10 Dose Modifications of Chemotherapeutic Drugs for Baseline Organ Dysfunction or Subsequent Treatment Cycles

For patients with baseline organ dysfunction within the allowed limits of the eligibility criteria, or for those who experienced \geq Grade 3 non-hematologic toxicities excluding neutropenic fever and infections during the first induction, a dose reduction is

recommended. The following dose modifications are suggested for all subsequent treatment cycles:

6.10.1 If a patient develops Grade ≥ 3 non-hematologic toxicity other than Grade 3 infections within 28 days from the last dose of G-CLAM, the next course of G-CLAM will be given once toxicity is $<$ grade 2. The following dose reductions can be considered: cladribine 4 mg/m² days 1-5, cytarabine 1.5 g/m² days 1-4, mitoxantrone at one dose level below initial regimen days 1-3, G-CSF dose unchanged, and sorafenib at one dose level below their initial regimen. Additionally, the mitoxantrone may be omitted entirely if a 2nd induction course is indicated (any response less than CR without MRD) per treating physician discretion in discussion with the PI. Assuming these doses are well-tolerated the first course of G-CLA will be administered at these doses, omitting mitoxantrone. If Grade ≥ 3 non-hematologic toxicity occurs again, there will be a further reduction in doses of cladribine to 3 mg/m² daily days 1-5 and cytarabine to 1 g/m² daily days 1-5 for the first cycle of G-CLA. Doses for subsequent courses of G-CLA will be discussed with the Principal Investigator. Patients who were receiving dose level -1 sorafenib or mitoxantrone when grade ≥ 3 toxicity occurred will be taken off study.

6.10.2 Mitoxantrone: Reduce mitoxantrone dose by 50% if the bilirubin concentration is 1.5-4.5 x IULN and to 25% if the bilirubin concentration is > 4.5 x IULN. As per 6.10.1 can omit mitoxantrone entirely if clinically indicated.

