14.0 STATISTICAL CONSIDERATIONS

14.1 Phase 1

14.1.1 General Considerations: DLTs are defined in Section 8.3. DLTs occurring during Cycle 1 will be used to guide dose escalation. However, before the phase 2 portion is begun, all grade ≥ 3 adverse events of all patients treated in the phase 1 portion will be reviewed to assess for late and cumulative toxicities that were not captured during the phase 1 portion of the trial. The Principal Investigator reserves the right to modify the protocol to reduce the drug doses identified in the phase 1 portion if this assessment suggests a significant risk of late/cumulative toxicities. Patients will be considered evaluable for DLT if they received at least 75% of the assigned doses of each chemotherapeutic during Cycle 1 or if they developed a DLT. If a patient does not develop a DLT but does not receive at least 75% of treatment during Cycle 1, the patient will be considered not evaluable for DLT and will be replaced. Maximum tolerated dose (MTD) is defined as the highest dose studied in which the incidence of DLT is $<33\%$ assuming at least 6 patients have been treated at this dose.

14.1.2 Dose Escalation scheme:

Starting with dose level K=1:

A. Evaluate 6 patients at dose level K

- a. If 0 or 1 have DLT, increase dose to K+1 and go to A
- b. If 2 have DLT, stop dose escalation
- c. If >2 have a DLT, go to dose K-1

The dose level below that which dose escalation was stopped is the potential MTD.

In order to better define safety and initial evidence of anti-leukemia activity while waiting for patients to complete their treatment cycles to assess the MTD, any dose level cohort may be expanded up to 12 patients, provided that

2 or fewer of 6 patients had DLT at that dose level (ie at least 4/6 have had no DLT). the cohort is expanded to 7-11 patients, these patients will not count toward DLT and MTD evaluation. If a cohort is expanded to 12 patients, the following rules will determine further dose escalation:

If 3 or fewer have DLT, increase dose to K+1 (go to A)

If 4 or more have DLT, stop dose escalation

Dose-finding for both mitoxantrone and sorafenib:

Level 1	Mitoxantrone10 mg/m ²	Sorafenib 200 mg BID
Level 2	Mitoxantrone12 mg/m ²	Sorafenib 200 mg BID
Level 3	Mitoxantrone15 mg/m ²	Sorafenib 200 mg BID
Level 4	Mitoxantrone18 mg/m ²	Sorafenib 200 mg BID
Level 5	Mitoxantrone18 mg/m ²	Sorafenib 400mg AM, 200 mg PM
Level 6	Mitoxantrone18 mg/m ²	Sorafenib 400 mg BID

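### Section 14.2 replaces phase 2 patients on the basis of Cycle 1 doses received and states no all-treated MRDneg CR analysis, so the primary rate can be biased upward by an amount that depends on an ambiguous rule

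*Combined protocol and SAP*

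**What the plan says.** The phase 2 evaluability rule in section 14.2 reads: "Patients will be considered not evaluable if they received less than 75% of the assigned doses of each chemotherapeutic agent during Cycle 1". Such patients are replaced. One exception follows, worded in these terms: "does not receive at least 75% of their assigned dose of sorafenib but discontinues the drug due to toxicity, they will be considered evaluable". No replacement is made in that case. The reason given is to capture the toxicity and its possible effect on efficacy.

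The phase 1 rule in section 14.1.1 is wider. It keeps patients who received "at least 75% of the assigned doses of each chemotherapeutic during Cycle 1 or if they developed a DLT". Section 14.2 has no such general toxicity clause.

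On schedule, section 6.3.1 says "Mitoxantrone will be given IV daily over 60 minutes Days 1-3 and sorafenib orally Days 10-19 for all levels", with a 2-day allowance either way. Cladribine and cytarabine run on Days 1-5 (section 6.4.1). Sections 6.3.5 and 6.4.5 state: "All treatment is given as intent-to-treat; missed doses will not be made up". This is a dosing instruction and does not define an analysis set. No section defines an all-treated or all-enrolled analysis of MRDneg CR.

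Section 6.6 places the first routine response marrow at count recovery or between Days +28 and +35, whichever comes first.

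**The concern.** In a single-arm trial judged by a response count, the denominator carries the inference. Here, membership depends on doses received after treatment starts. A patient who dies, withdraws consent or switches to other leukemia therapy early in Cycle 1 (sections 6.14.3 and 6.14.8), or whose IV drug is stopped for toxicity, may be taken out and replaced by someone who tolerated treatment better. Most such patients would have no response marrow and would normally count as non-responders.

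The exception shows that the plan recognises the problem, since it was written so that the effect of toxicity on efficacy is not lost. But it closes only the sorafenib-toxicity route. At stake is whether the rate set against 12/19 and 31/41 describes everyone who started the regimen. With no all-treated result planned, a reader could not judge the difference.

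**Working it through.** **1. Who can leave: three readings of the rule.**

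- *Every agent must be short.* Few patients qualify, because the IV drugs are complete by Day 5. The effect is close to nil.
- *Any one agent suffices, sorafenib not counted.* Mitoxantrone is at 2/3 = 66.7% after Day 2 and complete on Day 3. Cladribine and cytarabine are at 3/5 = 60% after Day 3 and 4/5 = 80% after Day 4. Only patients whose IV drugs are cut short leave. One missed mitoxantrone dose, or two missed cladribine or cytarabine doses, is enough.
- *Any one agent suffices, sorafenib counted.* After seven of ten days (through Day 16) a patient has had 70%. The Day 17 morning dose brings the total to 3000/4000 mg = 75% (levels 1-4), 4600/6000 mg = 76.7% (level 5) or 6000/8000 mg = 75% (level 6). Patients who leave before about Day 17 for a reason other than stopping sorafenib for toxicity can also drop out. The 2-day allowance means that Day 17 is approximate.

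The sorafenib exception favours the third reading, since it would be largely redundant if a sorafenib shortfall could not exclude a patient. The heading of section 6.10, "Dose Modifications of Chemotherapeutic Drugs for Baseline Organ Dysfunction or Subsequent Treatment Cycles", also covers sorafenib (6.10.5). Against this, other sections speak of sorafenib combined with chemotherapy, as if it were separate.

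**2. The plan's own figures.** Inputs from section 14.2: 19 patients in stage 1, continue at 12 or more; 22 further patients, success at 31 or more of 41; null rate 60%, alternative 80%.

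P(pass) = sum over x = 12 to 19 of Bin(x; 19, p) × P(Bin(22, p) ≥ 31 − x)

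| Quantity | Stated | Exact |
|---|---|---|
| Early termination at 60% | 51% | 51.2% |
| Average sample size at 60% | 29 | 29.7 |
| Power at 80% | 80% | 81.5% |
| Type I error at 60% | 10% | 2.7% |

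All but the type I error agree closely. That mismatch is a separate matter; here it means the rule has slack.

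**3. Effect of replacement.** Let f be the share of treated patients replaced and r the response rate they would have had. Neither is in the documents, so both are assumptions.

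Evaluable rate = (0.60 − f × r) / (1 − f)

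| f | r | Evaluable rate | P(pass) |
|---|---|---|---|
| 0 | – | 60.0% | 2.7% |
| 2% | 0 | 0.60/0.98 = 61.2% | 3.8% |
| 2% | 20% | 60.8% | 3.4% |
| 2% | 40% | 60.4% | 3.0% |
| 5% | 0 | 0.60/0.95 = 63.2% | 6.4% |
| 5% | 20% | 62.1% | 4.9% |
| 5% | 40% | 61.1% | 3.7% |
| any | 60% | 60.0% | 2.7% |

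With r = 0, P(pass) reaches 10% only at f of about 7.7%.

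If the true all-treated rate is 68%, the historical figure, and r = 0, P(pass) goes from 19.0% to 24.5% (f = 2%) or 35.0% (f = 5%).

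**4. In patients.** The expected number replaced per 41 evaluable is 41 × f/(1 − f): 0.8 at 2% and 2.2 at 5%. At the passing boundary, 31/41 = 75.6%. With one replaced failure it is 31/42 = 73.8%, and with two it is 31/43 = 72.1%.

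**The case against.** Read literally, the rule requires a shortfall on each agent, which would remove almost nobody. If sorafenib is not chemotherapy, patients who die or withdraw after Day 4 with full IV dosing stay in. Even if sorafenib counts, a patient who starts it and stops for toxicity, including toxicity that proves fatal, is arguably retained. Deaths after about Day 17 stay in too. The commonest failures (resistant disease, MRD-positive remission, incomplete count recovery) reach the marrow assessment and are counted. Nothing in the documents shows that Cycle 1 doses are often missed. Early deaths also appear in overall survival, which section 8.5 follows for all patients.

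Much of this stands. It limits the likely size and makes it conditional on the reading. It does not remove the problem: on any reading some post-treatment events can take a likely failure out of the denominator, and overall survival does not replace an all-treated MRDneg CR rate.

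A reader might infer that the 5% treatment-related mortality shown in Appendix A for scores below 13.11 gives the replaced share. It does not. The table gives no timing, some of those deaths would be retained, and withdrawals are not covered. The 5% used above is only an illustration.

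**Conclusion.** The concern holds in direction, not in a known amount. Section 14.2 makes the primary denominator depend on treatment received, closes only one route by which likely failures leave, and plans no all-treated result. If replaced patients respond less often than the rest, the reported rate is too high.

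A reader might go further and conclude that the stated 10% type I error is broken. The documents do not support that. The rule as written has an exact error of 2.7%, and 10% is passed only if more than about 7.7% of treated patients are replaced and all are failures. At assumed shares of 2% and 5%, all failures, the error is 3.8% and 6.4%. It is lower if some replaced patients would have responded, and unchanged if replacement is unrelated to response.

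The point should be fixed, with medium confidence: the text is clear that patients are replaced, but unclear on how many the rule would catch.

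**What to change.** In section 14.2:

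- Make the primary set all eligible patients who start protocol therapy at the phase 2 dose, including phase 1 patients treated at that dose. Count anyone without a documented MRDneg CR within two courses as a non-responder, and do not replace patients.
- Report the 75%-dose set as a sensitivity analysis, with the number of exclusions and the reason for each. State for that set whether a shortfall on any agent or on every agent excludes a patient, and whether sorafenib counts.
- State that 60% and 80% are all-treated rates. Report the historical 68% with its basis (57 of 61 patients evaluable), because a comparison needs both rates on the same footing. The documents do not give outcomes for the other four.

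The 75% rule can remain for DLT evaluability in phase 1.

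The cost is a few sentences and no new data. The observed rate may be slightly lower. Power stays at 81.5% if 80% is an all-treated rate. If 80% was meant among evaluable patients only and all replaced patients fail, the all-treated rate is 0.80 × (1 − f). With the same cut-offs, power is then about 74% at 2% (rate 78.4%) and 60% at 5% (rate 76.0%), so the sponsor should decide which was intended.
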